2.2.2 RESIDENT/PATIENT LEVEL

Inclusion criteria:

Geriatric patients (≥ 65 years) admitted to geriatric wards of participating hospitals or residents of participating nursing homes can be included if the following criteria are met:

- (1) Being incontinent of urine and stool
- (2) Expected minimum length of stay of 14 days
- (3) Intact skin with no clinical signs of IAD

OR

Intact skin with early clinical signs of IAD (erythema) but without clinical signs of infection (GLOBIAD category 1 A)

- (4) Written informed consent (by legal representative, if required)

Exclusion criteria:

- (1) Residents/patients at the end of life
- (2) Residents/Patients with skin loss due to IAD (GLOBIAD category 2 A) and/or signs of clinical infection in the IAD area (GLOBIAD category 1 B, category 2 B)
- (3) Any other skin condition or wounds (at investigational areas of the skin) requiring additional treatment (including but not limited to pressure ulcers, intertrigo, infection)
- (4) Known hypersensitivity or allergy to silicones and/or topical leave-on products
- (5) Topical treatments in the IAD area.

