2.3.2 CRITERIA FOR DISCONTINUING

Nursing home/hospital level:

- (1) If the institution no longer wants to participate,
- (2) Any circumstance that makes it impossible or irresponsible to continue study at the respective institution

Resident/patient level:

- (1) If a participant or its legal representative withdraws its consent,
- (2) Adverse events (AEs) that, in the judgment of study personnel, interfere with further participation in the trial,
- (3) Serious adverse events (SEAs),
- (4) Incidents that, in the judgment of study personnel, interfere with further trial participation,
- (5) Serious incidents,
- (6) The occurrence of a medical condition which is incompatible with continued trial participation.

These include, for example:

- a. Mycotic or bacterial inflammation, or other skin conditions in the study area that require topical (drug) treatment of the skin area with other products,
 - b. The development of a category II, III, IV pressure ulcer, or an unstageable pressure ulcer, or a suspected deep tissue injury (DTI)
- (7) If participants are permanently transferred outside the study site
 - (8) In the intervention groups: missing application of study products for more than 72 hours
 - (9) More than three missing study visits

An "adverse event" or "serious adverse event" is in accordance with the definitions of Regulation (EU) 2017/745 (MDR) as defined in Article 2(57) and (58). An "incident" or "serious incident" is in accordance with the definitions of Regulation (EU) 2017/745 (MDR) as defined in Article 2(64) and (65).

For the whole trial:

- (1) If the ethics committee withdraws the ethics approval
- (2) If after 8 months of recruitment less than $n = 60$ participants have been included
- (3) The CTAB unanimously decides after 8 months that study continuation is not suitable to answer the research questions.

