2.7 OUTCOMES AND VARIABLES

Because of the exploratory nature of the trial and according to methodological guidance for exploratory trials, a distinction between primary and secondary endpoints is not made [23]. Because the main aim is to prevent IAD, IAD incidence is likely to be considered as a primary outcome in a possible subsequent confirmatory trial.

Table 2: Outcomes and variables per participant

Outcome Name	Device/Measurement instrument/Scale and metric	Time points	Response Options/Categories/ Range
IAD incidence	
 • IAD Classification according to GLOBIAD [24] and distinction between intact and eroded skin according to Proceedings of the Global IAD Expert Panel [10] • Cumulative incidence • IAD Localization according to the following definition: 
 ○ Back: Sacral region going down to the upper thighs, bordered approximately 5 cm below the gluteal fold ○ Front: Navel to upper thigh 	Days 0, 2, 4, 6, 8, 10, 12, 14	
 • Presence of IAD: 
 (1) None; (2) Category 1 A; (3) Category 1 B; (4) Category 2 A; (5) Category 2 B • Localization of IAD: 
 (1) Back (2) Front
Erythema	
 • Rating according to the item 'Redness' of the incontinence-associated dermatitis and its severity (IADS) instrument [25] • 3-Item-Scale (ordinal) 	Days 0, 2, 4, 6, 8, 10, 12, 14	
 • Redness: 
 (1) None; (2) Pink; (3) Red/Bright red

Outcome Name	Device/Measurement instrument/Scale and metric	Time points	Response Options/Categories/ Range
	
 • Mexameter MX18 with MDD 4 (Courage + Khazaka Electronic GmbH) [26] (measurements according to SOP „Mexameter® MX 18“ Version 1.0, 18.05.2022) (see Fehler! Verweisquelle konnte nicht gefunden werden.) • Arbitrary units (AU) from 0 (= no erythema) to 999 (= extreme erythema) • Means of duplicate measurements at the cranial end of the gluteal cleft 	Days 0, 2, 4, 6, 8, 10, 12, 14	
 • Erythema level: 0 - 999 [numeric; AU]

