2.7.1 INITIAL SKIN ASSESSMENT

At the baseline visit on day 0, a skin assessment is performed to check and document the initial condition of the skin in the study area. It will be documented whether an IAD (classified according to GLOBIAD [25]) is already present and if the skin is intact or eroded (according to *Proceedings of the Global IAD Expert Panel* [35]). Other dermatological conditions in the study area will also be documented.

Study participation with pre-existing IAD is only possible if it is a mild form with early signs of IAD and intact skin (GLOBIAD category 1 A). If the initial skin assessment reveals a moderate or severe form (including skin loss or clinical sign of infection) of IAD (GLOBIAD category 1 B; 2 A or 2 B), the participant will be excluded. Other dermatological conditions or skin affections (at investigational areas of the skin) requiring dermatological treatment or interfering with the conduct of the study also lead to exclusion.

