4.2 Outcome variables

Because of the exploratory nature of the trial and according to methodological guidance for exploratory trials, a distinction between primary and secondary endpoints is not made [23]. The presence of IAD is, however, with consideration of the study protocol considered as main outcome variable, i.e. primary outcome.

Variables marked with (day0) will be considered as baseline data. All outcome variables are measured in eight study visits in total (one baseline visit [Day0] and seven follow-up visits [Day2, Day4, ..., Day14]).

Characteristic	eCRF table	Variable name	Type	Scale	Comment/Analysis
IAD incidence	mnppid_skin				Main outcome Measured via occurrence of IAD at given visit (skin_0011)
IAD present?		skin_0011	cat	0-no 1-yes	n (%)
Location front		skin_0015	cat	0-no 1-yes	n (%)
Location back		skin_0016	cat	0-no 1-yes	n (%)
GLOBIAD category (front)		skin_0012	cat	1-1A 2-1B 3-2A 4-2B	n (%) (check skin_0015)
GLOBIAD category (back)		skin_0017	cat	1-1A 2-1B 3-2A 4-2B	n (%) (check skin_0016)
Erythema (visual)					Multi variable
"Redness?"		skin_0021		0-None 1-Pink 2-Red/bright red	main focus if available, else build variable based on 0026, 0027a and 0028a; (highest level counts) n (%)
n.a.		skin_0023		0-no 1-yes	Check if contradicts skin_0026, 0027a and 0028a
None		skin_0026		0-no 1-yes	
Pink		skin_0027a		0-no 1-yes	
Front		skin_0027b		0-no 1-yes	n (%)
Back		skin_0027c		0-no 1-yes	n (%)
Red/bright red		skin_0028a		0-no 1-yes	
Front		skin_0028b		0-no 1-yes	n (%)
Back		skin_0028c		0-no 1-yes	n (%)
Erythema level (1)		Func_0081 (day0) func_0141	Numeric	Arbitrary units (AU) from 0 (= no erythema) to 999 (= extreme erythema)	Mean (sd) check func_0082 func_0142, func_0143
Erythema level (2)		Func_0083 (day0) func_0144	Numeric	Arbitrary units (AU) from 0 (= no erythema) to 999 (= extreme erythema)	Mean (sd) check func_0084

Characteristic	eCRF table	Variable name	Type	Scale	Comment/Analysis
					func_0145, func_0146
Erythema level (total)			Numeric	Arbitrary units (AU) from 0 (= no erythema) to 999 (= extreme erythema)	Mean (sd) of (Erythema level 1 + Erythema level 2)/2
Erosion					
"Erosion present?"		skin_0041		0-no 1-yes	n (%)
Front		skin_0044		0-no 1-yes	n (%)
Back		skin_0045		0-no 1-yes	n (%)
Maceration					
"Maceration present?"		skin_0051		0-no 1-yes	n (%)
Front		skin_0054		0-no 1-yes	n (%)
Back		skin_0055		0-no 1-yes	n (%)
Local intolerances					
Have any local intolerances occurred since the last visit?		skin_0061		0-no 1-yes	n (%)

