4.4 Efficacy

The main efficacy variable is the IAD cumulative incidence measured by IAD presence on each visit day (Day0, Day2, ..., Day14). Secondary efficacy variables are Erythema and Maceration level, IAD itch and pain level and patient satisfaction.

- IAD-related itch and pain level (numeric rating scale) are measured at each visit day (Day0, Day2, ..., Day14) if IAD is present and if MMSE \geq 24.
- IAD itch and pain level (PAINAD-G) are measured at each visit day (Day0, Day2, ..., Day14) if IAD is present and if MMSE < 24.
- Patient satisfaction is measured at each visit day (Day0, Day2, ..., Day14) if MMSE \geq 24
- Erythema and Maceration level are measured at each visit day (Day0, Day2, ..., Day14).

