7.2 Analyses of endpoints

Because of the exploratory nature of the trial and according to methodological guidance for exploratory trials, a distinction between primary and secondary endpoints is not made [23]. Because the main aim is to prevent IAD, IAD incidence is likely to be considered as a primary outcome in a possible subsequent confirmatory trial and is therefore considered as primary efficacy variable.

For all outcomes, total group differences are reported by the corresponding effect size based on the statistical models as outlines below and corresponding 95% confidence intervals. Relevant timepoints will be Day 6 and Day14. Day0 reports will be presented as is.

The relevant blinded group comparisons are: A vs. B; A vs. C; B vs. C.

For cumulative incidence rates of IAD, Kaplan-Meier Curves will be presented with time ranging from inclusion to IAD onset, i.e. the first occurrence of IAD 2A or 2B. Censoring occurs if patients withdraw from the study before the onset of an IAD or if the study is terminated before IAD onset. Mixed effects Cox regression model (shared frailty model) will be carried out for group comparisons of incidence rates. The latter includes group allocation, sex, setting (nursery home, geriatric hospital ward) and time (continuous) as fixed effects and random intercepts for the ward and the patients. The resulting Hazard ratios for IAD will be presented. Potential non-linear time effects will be explored and modelled using fractional polynomials or splines.

Group differences for categorical, dichotomous responses are calculated by estimating group effects from either generalized linear mixed-effects models (binary logistic) - including particular baseline status (maceration, IAD-related itch), group allocation, sex, setting and time as fixed effects and random intercepts per ward and patients - or nonparametric analysis of longitudinal data depending on the distribution of the data. For the Erosion model, no baseline adjustment is considered due to its presence is an exclusion criterion.

List:

- Erosion (no/ yes)
- Maceration (no/ yes)
- IAD related itch (no/ yes) [only measured if IAD present]
- IAD-related pain (no/yes) [only measured if IAD present]

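### IAD incidence means any IAD in SAP 4.2 and 4.4 but first 2A or 2B in SAP 7.2, and worsening from 1A to 1B is an event in no time-to-event analysis

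*Combined protocol and SAP*

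**What the plan says.** - **SAP 4.2 (outcome table).** IAD incidence is entered as "Main outcome Measured via occurrence of IAD at given visit (skin_0011"), a no/yes item for any category.
- **SAP 4.4.** "The main efficacy variable is the IAD cumulative incidence measured by IAD presence on each visit day", and the list of days starts at Day 0.
- **SAP 7.2.** For the cumulative incidence of IAD, the Kaplan-Meier curves use "time ranging from inclusion to IAD onset, i.e. the first occurrence of IAD 2A or 2B". The mixed-effects Cox model then compares the groups on the same incidence rates. Withdrawal before onset is censored.
- **Protocol 4.3.** It plans the same curves to the onset of IAD, with no limit on category.
- **Protocol 2.7, Table 2.** The recorded scale is "(1) None; (2) Category 1 A; (3) Category 1 B; (4) Category 2 A; (5) Category 2 B", so 1B is a category of its own at every visit.
- **Protocol 2.2.2 and 2.7.1.** Participants may enter with no IAD, or with "Intact skin with early clinical signs of IAD (erythema) but without clinical signs of infection (GLOBIAD category 1 A"). Entry is barred for a "moderate or severe form (including skin loss or clinical sign of infection) of IAD (GLOBIAD category 1 B; 2 A or 2 B").
- **Protocol 2.3.2.** One example of a condition that ends participation is "Mycotic or bacterial inflammation, or other skin conditions in the study area that require topical (drug) treatment of the skin area with other products".
- **SAP 7.3.** A second time-to-event analysis counts any category, 1A and 1B included, but only in participants without IAD at baseline.

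**The concern.** The primary objective (SAP 1.1.1) is to compare IAD incidence between arms and to supply effect sizes for a later confirmatory trial. Both uses need a single event. As written, a report could give a cumulative incidence of any IAD beside a hazard ratio for 2A or 2B, both labeled IAD incidence, and a later sample size calculation could combine the two.

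There are two further problems. Counting baseline 1A as a case mixes prevalent disease into an incidence. And category 1B, which the protocol treats like 2A and 2B at entry, drops out of the main time-to-event analysis. Participants whose infection ends their participation may then be censored for a reason linked to the outcome.

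**Working it through.** The SAP states no incidence for any GLOBIAD category, so there is no planned figure to reproduce. The check sets the rules side by side and then shows, on assumed rates, what depends on them.

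**Step 1. How each rule treats the same course.**

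| Course over 14 days | SAP 4.2/4.4 (any IAD present) | SAP 7.2 (first 2A or 2B) | SAP 7.3 second analysis |
|---|---|---|---|
| No IAD, then 1A | case | non-event | event |
| No IAD, then 1B | case | non-event | event |
| No IAD, then 2A or 2B | case | event | event |
| 1A at entry, stays 1A | case from Day 0 | non-event | not included |
| 1A at entry, then 1B | case from Day 0 | non-event, or censored if discontinued | not included |
| 1A at entry, then 2A or 2B | case from Day 0 | event | not included |

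The rules agree only for participants who enter without IAD and reach 2A or 2B. The fifth row is an event in neither time-to-event analysis.

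**Step 2. What counting Day 0 does.** Let s be the share of an arm enrolled with 1A, and p the 14-day risk of any IAD in the rest. Read literally, the cumulative incidence under 4.4 is s + (1 − s)p. It cannot fall below s. With equal s in two arms, the risk difference is (1 − s)(p₁ − p₀), which is smaller than the difference among those at risk. Randomization is stratified by sex, with separate lists by setting (protocol 3.1), and not by skin condition. A chance imbalance in s would therefore enter the comparison directly. The documents do not give s.

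**Step 3. How much could hang on 1B.** All rates here are assumptions. Take a 14-day risk p₂ of 2A/2B from 5% to 20% and a 14-day risk p_B of 1B from 1% to 10%, with constant independent hazards H₂ = −ln(1 − p₂) and H_B = −ln(1 − p_B).

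- Risk of first 1B, 2A or 2B: 1 − exp(−(H₂ + H_B)) = 1 − (1 − p₂)(1 − p_B).
- Share of first failures that are 1B: H_B / (H₂ + H_B).

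| p₂ | p_B | Risk, 2A/2B only | Risk, 1B/2A/2B | Share of first failures that are 1B |
|---|---|---|---|---|
| 5% | 1% | 5.0% | 5.9% | 16% |
| 5% | 10% | 5.0% | 14.5% | 67% |
| 10% | 1% | 10.0% | 10.9% | 9% |
| 10% | 5% | 10.0% | 14.5% | 33% |
| 10% | 10% | 10.0% | 19.0% | 50% |
| 20% | 1% | 20.0% | 20.8% | 4% |
| 20% | 10% | 20.0% | 28.0% | 32% |

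For the planned 60 per arm at p₂ = 10%, that is 6.0 events against 6.5 to 11.4.

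**Step 4. Effect on the hazard ratio.** Assume a hazard ratio of 0.5 for 2A/2B and HR_B for 1B. The ratio for the combined event is (0.5·H₂ + HR_B·H_B) / (H₂ + H_B).

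- HR_B = 0.5: 0.50 throughout.
- HR_B = 1.0: 0.52 to 0.84.
- HR_B = 2.0: 0.56 to 1.51.

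These figures compare two endpoints. They do not measure bias from censoring, which would also need the number of 1B participants discontinued.

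**Step 5. Censoring.** SAP 2.2 analyzes participants only until discontinuation, and 7.2 censors withdrawal before onset. SAP 5.1 imputes missing outcomes in all analyses under MAR or MCAR. The SAP does not say which of these governs the time-to-event outcome.

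**The case against.** The strongest defense is that 2A/2B is a coherent choice. It marks skin loss, and protocol Table 2 itself separates intact from eroded skin. Every eligible participant is free of 2A and 2B at Day 0. The grouping in protocol 2.7.1 is an entry rule, not an outcome definition. This stands: the documents do not show that 2A/2B is the wrong event. What they lack is a reason for using it in one section and any IAD in two others, or for leaving out 1B, which eligibility rules out at Day 0 just as firmly.

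It can also be said that SAP 4.2 treats Day 0 as baseline and 7.2 presents Day 0 as is, so the authors may never have meant to count 1A at entry as incident. That is plausible. But 4.4 lists Day 0 among the days that define the main variable, and no sentence removes prevalent cases. The baseline-1A interaction in 7.3 does not change the event.

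A reader might infer three stronger points that the text does not support:

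- **That 1A-to-1B worsening is recorded nowhere.** SAP 4.2 tabulates GLOBIAD category, front and back, as n (%), and SAP section 7 reports each time point. The gap is confined to the time-to-event analyses.
- **That reaching 1B means being censored.** The trigger in protocol 2.3.2 is a need for other topical treatment. A participant with 1B who stays in the study remains at risk and can still reach 2A or 2B.
- **That the hazard ratios are biased by a known amount.** No 1B rate is given. If 1B is rare, or the treatment effect on it is the same, little changes. SAP 5.1 does plan to use drop-out reasons to judge whether data are missing not at random, though not specifically for this outcome.

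**Conclusion.** Wrong as written, and it should be fixed. Followed literally, the SAP counts prevalent 1A as incidence in one place and reports a different event under the same name in another. Worsening from 1A to 1B is an event in no time-to-event analysis. These conclusions rest on the text alone.

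The consequence for the results cannot be sized. The 4–67% share of first failures and the range of hazard ratios depend wholly on assumed risks and effects. Outcome-related censoring is a possibility created by reading protocol 2.3.2 with SAP 7.2, not a demonstrated bias. The trial is exploratory, without confirmatory tests, so no error rate is at stake. What is at stake is the effect size it was set up to supply.

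**What to change.** 1. State one incident-event definition under which all participants are event-free at Day 0. Use it in SAP 4.2, 4.4 and 7.2 for cumulative incidence, Kaplan-Meier and Cox. State that 1A at baseline is not an incident case, and note the difference from protocol 4.3.
2. Run the time-to-event analysis in the whole full analysis set for first 1B, 2A or 2B and for first 2A or 2B. Name which is main and which is sensitivity before the permuted arm labels in SAP 4.1 are decoded. Keep the any-IAD analysis of 7.3 in participants without IAD at baseline.
3. In at least a sensitivity analysis, treat discontinuation for infection in the IAD area as an event or a competing event, not only as independent censoring. Say whether the imputation in 5.1 applies to the time-to-event outcome.

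The clinical discontinuation rule is not questioned; only its statistical handling has to be reconciled with 7.2. The cost is SAP wording and one further model run. GLOBIAD category is recorded at every visit, and the eCRF has fields for early-termination reasons, so no new data are needed.

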4.1.1 SKIN ASSESSMENT

The skin assessments visits will be performed at Days 0, 2, 4, 6, 8, 10, 12 and 14. This will be performed by GCP-trained members of the study team. Nursing home residents/patients in geriatric hospitals/wards will be assisted to undress at the area of interest. In close cooperation with the caregivers, this will be ideally combined with the scheduled regular general basic care procedures, clothing changes or medical procedures.

The variables regarding IAD categorization, erythema, erosion and maceration will be documented by the blinded assessor. In case that a dermatological/medical condition is detected which is, in the opinion of the assessor, incompatible with further study conduct, participation for this subject will be terminated with specification of the underlying reason

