7.3 Planned subgroup analyses

Differential treatment effects will be analyzed by including interaction terms for subgroups by intervention group. Prespecified subgroups include sex (male/female) and patients with and without IAD 1A status at baseline. For the subgroup consisting of no initial IAD, a second time-to-event analysis will be realized, using the first occurrence of any IAD category as event and thus including 1A and 1B. Additionally, location (front/back) of IAD and Erosion will be considered for subgroup analyses as well. Parallel to interaction effects estimated marginal treatment effects of the subgroups and 95% CI will be reported.

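### The Cox model for IAD onset contains a time effect it cannot estimate and a patient frailty it barely can, so its hazard ratios depend on coding that the SAP leaves open

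*Combined protocol and SAP*

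**What the plan says.** SAP 7.2 states: "Mixed effects Cox regression model (shared frailty model) will be carried out for group comparisons of incidence rates". Besides group, sex and setting, the model has "time (continuous) as fixed effects and random intercepts for the ward and the patients". It adds: "Potential non-linear time effects will be explored and modelled using fractional polynomials or splines". The event is "the first occurrence of IAD 2A or 2B", so a patient contributes at most one. The output is fixed as well: "The resulting Hazard ratios for IAD will be presented". The Table 2 shell in SAP 10.2 lists hazard ratios for arm and sex.

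SAP 7.3 adds a second time-to-event analysis in patients without IAD at baseline, "using the first occurrence of any IAD category as event and thus including 1A and 1B". It names no other model.

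SAP 4.2 gives the observation grid as "one baseline visit [Day0] and seven follow-up visits".

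The SAP does not state the data layout (one row per patient or per visit), the frailty distribution or the handling of ties. Time is written as a main effect; no group-by-time term appears.

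**The concern.** In a Cox model the unspecified baseline hazard already carries all dependence on time, so there is nothing left for a main effect of time to estimate. A random intercept per patient needs repeated information on each patient, and a first-event analysis gives one outcome each. The same terms (time, ward intercept, patient intercept) appear in the longitudinal mixed models that SAP 7.2 specifies for the other outcomes, where they are legitimate.

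Estimating effect sizes for a possible confirmatory trial is part of the primary objective (SAP 1.1.1), and SAP 7.2 treats IAD incidence as the primary efficacy variable. If the hazard ratio changes with a coding choice that the plan does not fix, the planning estimate is not pre-specified.

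**Working it through.** The documents give no event rate, target effect or power for this model, so there is no figure of the plan's to reproduce.

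**Inputs from the documents.** 220 patients in 20 sites (25 in 2 hospital units, 195 in 18 nursing homes; SAP 3). Allocation 1:1:1 (SAP 1.2). Seven follow-up visits: "The skin assessments visits will be performed at Days 0, 2, 4, 6, 8, 10, 12 and 14" (Protocol 4.1.1). Inflation from 60 to 70 per group (SAP 6), which implies a loss of 10/70 = 14.3%.

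**Assumed, not in the documents.** 14-day control risk 10%, 20% or 35%; true hazard ratio 0.50 in both active arms; ward SD 0.3 on the log hazard; drop-out 14%.

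**Step 1: time with one row per patient.** With arm effect β and time coefficient γ, patient i failing at t_i contributes

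exp(βx_i + γt_i) / Σ_{j: t_j ≥ t_i} exp(βx_j + γt_j) = exp(βx_i) / Σ_{j: t_j ≥ t_i} exp(βx_j + γ(t_j − t_i)).

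Every t_j − t_i is zero or positive. The denominator therefore shrinks as γ falls, and the likelihood rises without limit on γ. In the limit each failure is compared only with patients whose follow-up ended at the same visit, so most of the valid risk set is lost. This needs no assumption about event rates.

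In simulation the likelihood was monotone in γ in 100% of trials. The arm hazard ratio stayed finite (|log HR| above 5 in 1% of trials or fewer) but moved towards 1. Both fits used Breslow ties and left out the ward term:

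| Control risk | Mean events | Median HR without time | Median HR with time | Ratio |
|---|---|---|---|---|
| 10% | about 14 | 0.43 | 0.58 | 0.58/0.43 = 1.35 |
| 20% | about 29 | 0.48 | 0.65 | 0.65/0.48 = 1.35 |
| 35% | about 52 | 0.51 | 0.74 | 0.74/0.51 = 1.45 |

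The 0.43 in the first row comes from very few events per arm.

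**Step 2: time with one row per visit.** Visit day is the same for everyone in a risk set, so exp(γt_i) is a common factor in numerator and denominator and cancels. Numerically, the log partial likelihood changed by less than 2e-12 for γ from −20 to 20. γ is not identifiable, and the arm hazard ratio is unchanged. Splines or fractional polynomials of time behave the same way.

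**Step 3: patient intercept with one event each.** This applies in both layouts. With a gamma frailty of variance θ, marginal survival is S(t|x) = (1 + θH(t)e^{βx})^(−1/θ). An event in the interval up to visit k contributes S(t_{k−1}) − S(t_k); a censored patient contributes S(t_k). Here θ is separated from β only through departures from proportional hazards across seven visits. The profile over θ from 0 to 10 (ward effect left out of the fit, 58 to 60 usable trials per row) gave:

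| Control risk | True patient SD | Median log-likelihood range | Trials with every θ inside the 95% region (within 1.92) | Best θ at 0 or 10 | Median HR, θ = 0 to θ = 10 |
|---|---|---|---|---|---|
| 10% | 0 | 0.15 | 100% | 57 of 58 | 0.51 to 0.39 |
| 10% | 1 | 0.36 | 98% | 55 of 60 | 0.49 to 0.35 |
| 20% | 0 | 0.36 | 97% | 49 of 60 | 0.49 to 0.39 |
| 20% | 1 | 0.75 | 88% | 45 of 60 | 0.58 to 0.30 |
| 35% | 0 | 1.10 | 78% | 43 of 60 | 0.56 to 0.29 |
| 35% | 1 | 0.92 | 77% | 38 of 60 | 0.56 to 0.30 |

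The data hardly distinguish the values of θ, while the conditional hazard ratio drifts away from 1 as θ grows, even when no patient frailty was simulated.

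**Step 4: ties.** All onsets fall on seven visit days, so ties are heavy. They do not make a Cox model wrong, but the method of handling them should be named.

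**The case against.** The strongest reply is that the bias in Step 1 needs a layout the SAP never states. SAP 4.2 and 4.4 describe IAD as recorded at each visit, and a patient intercept suggests several rows per patient. On that reading, time is a redundant term that leaves the arm hazard ratio alone. This stands, and the shift towards 1 must be reported as conditional on one row per patient. It does not make the specification correct: a term that either distorts the result or is empty should not be in the model, and the patient intercept remains a problem in both layouts.

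The sizes rest on assumed event rates, drop-out and effect. This also stands. The monotone likelihood and the cancellation do not depend on those assumptions.

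The trial is exploratory, and IAD incidence is also described by Kaplan-Meier curves and cumulative incidences (SAP 7 and 7.2) and by differences in proportions with confidence intervals (Protocol 4.3), none of which uses this model. That is true and limits the damage, but it does not repair the hazard ratios that SAP 7.2 and the Table 2 shell promise.

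Finally, if a discrete-time hazard model was intended, a time term would be right. The text, however, says Cox.

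**Conclusion.** The specification is wrong as written, not merely incomplete. No layout allows a main effect of time to be estimated in this Cox model, and the patient frailty variance is barely identifiable with at most one event per patient.

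The consequence depends on coding. With one row per patient, the median arm hazard ratio moved from 0.43–0.51 to 0.58–0.74 under the stated assumptions. With one row per visit, the time term has no effect. In either layout the patient intercept makes the conditional hazard ratio depend on a variance the data hardly inform, and it pushes in the opposite direction, away from 1.

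A reader might go further and infer that the likelihood as a whole is degenerate and the arm hazard ratios are bound to be wrong or non-estimable. The documents do not support that: the layout is open, only the time coefficient diverges, the arm hazard ratio stayed finite in nearly all simulated trials, and the frailty likelihood is nearly flat rather than degenerate. What is at risk is the quality of the hazard ratios carried into planning the next trial; the plan makes no confirmatory test.

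**What to change.** In SAP 7.2, delete from the Cox model the main effect of time, the sentence on splines and fractional polynomials, and the patient random intercept. Keep arm, sex and setting as fixed effects with a frailty at ward level only, use Efron's method for ties, and state the data layout. Apply the same model to the second time-to-event analysis in SAP 7.3.

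Alternatively, replace it with a discrete-time model on person-visit rows: binomial, complementary log-log link, visit time (as a factor or a smooth term) as the baseline hazard, arm, sex and setting as fixed effects, and a random intercept for ward only. Here a time term is legitimate, and a smooth one may be steadier than seven visit levels if events are few.

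If the intention was to allow for non-proportional hazards, write a group-by-time term instead of a main effect.

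The cost is a few sentences of SAP text and a few lines of R. No new data are needed.
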